- Two 0.1 mL sprays for 20 kg to less than 40 kg; or
- Two 0.2 mL sprays for patients weighing 40 kg or more.

References:

1. Malamed SF, Handbook of Local Anesthesia, 5 th Edition, Elsevier Mosby, St.Louis
2. Bennett CR. Monheim's local anesthesia and pain control in dental practice, 7th ed. St. Louis, Mosby
3. Eloesser L. Recent advances in regional (local) anesthesia. Cal State Med. J. 1912;10:90-7

8. FDA Approved Drug Products. Available at:

<http://www.accessdata.fda.gov/scripts/cder/drugsatfda/index.cfm?fuseaction=Search.DrugDetails>[last accessed 13 July 2016]

Specific Aims:

With the ability to avoid the traditional painful injection Kovanaze offers promise in the field of maxillary anesthesia and this study intends to:

1. Compare Kovanaze to conventional needle anesthetic in different settings (procedures other than fillings and/or involving multiple teeth) in adults and children (at least 6 years of age and weighing > 20 kg)
2. Evaluate patient anxiety, tolerance and acceptability of Kovanaze in patients undergoing dental procedures

Location:

The study will be conducted in three departments in VCU School of Dentistry; General Practice, Endodontics and Pediatric Dentistry and will explore the effectiveness of Kovanaze in different populations and circumstances.

Inclusion and Exclusion Criteria:

Inclusion Criteria:

- Pathology in the maxillary permanent (incisors, canines and premolars) or deciduous (incisors, canines and molars) teeth that require treatment under local anesthesia
- American Society of Anesthesiologists Class I or II

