The Modified Dental Anxiety Scale (MDAS) consists of 5 questions each with a 5-category rating scale, ranging from 'not anxious' to 'extremely anxious'. This answering scheme is a simplified rating system in comparison with Corah's Dental Scale that was an early 4-question measure of dental anxiety. The MDAS has an extra item about the respondent's anxiety to a local anesthetic injection that is particularly relevant for this study. (Humphris et al). Cut off is 19 or above (out of 25) for questions 1-5, which indicates a highly dentally anxious patient, possibly dentally phobic. Questions 6-8 are specific to this study to assess the effect of Kovanaze on dental anxiety.

CAN YOU TELL US HOW ANXIOUS YOU GET, IF AT ALL, WITH YOUR DENTAL VISIT BY INSERTING 'X' IN THE APPROPRIATE BOX?

- 1. If you went to your Dentist for TREATMENT TOMORROW, how would you feel?**

Not *Slightly* *Fairly* *Very* *Extremely*
Anxious *Anxious* *Anxious* *Anxious* *Anxious*

2. If you were sitting in the WAITING ROOM (waiting for treatment), how would you feel?

Not *Slightly* *Fairly* *Very* *Extremely*
Anxious *Anxious* *Anxious* *Anxious* *Anxious*

3. If you were about to have a TOOTH DRILLED, how would you feel?

Not *Slightly* *Fairly* *Very* *Extremely*
Anxious *Anxious* *Anxious* *Anxious* *Anxious*

4. If you were about to have your TEETH SCALED AND POLISHED, how would you feel?

Not *Slightly* *Fairly* *Very* *Extremely*
Anxious *Anxious* *Anxious* *Anxious* *Anxious*

5. If you were about to have a LOCAL ANAESTHETIC INJECTION in your gum, above an upper back tooth, how would you feel?

Not *Slightly* *Fairly* *Very* *Extremely*
Anxious *Anxious* *Anxious* *Anxious* *Anxious*

4. Satisfaction Questionnaire (for KOVANAZE Participants only)

These questions are to be administered at the end of the study visit to participants in Kovanaze arm only:

1. Have you ever experienced a LOCAL ANESTHETIC INJECTION in your gum, for dental treatment?

Yes No

2. When was the last time you received a LOCAL ANESTHETIC INJECTION in your gum?

> 1 year 6 months ago Less than a month ago

3. Compared to INJECTION, how effective do you think was NASAL SPRAY ANESTHETIC in reducing your anxiety and comfort during dental procedure?

Not Effective Slightly Effective No Difference Very Effective Extremely Effective

4. How likely is it that you would ask your dentist for a NASAL SPRAY ANESTHETIC, for your future treatment needs (compared to needle anesthetic)?

Never No preference Every time

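### Satisfaction item 3 cannot be interpreted as printed: it joins anxiety with comfort, mixes two kinds of response label, and has no option for a spray that was worse than injection

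*Combined protocol and SAP*

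**What the plan says.** Specific Aim 2 is to "Evaluate patient anxiety, tolerance and acceptability of Kovanaze in patients undergoing dental procedures". The satisfaction questionnaire is listed among the adult secondary outcome measures, with the instruction "These questions are to be administered at the end of the study visit to participants in Kovanaze arm only". Four of its features matter here.

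- Item 1 asks: "Have you ever experienced a LOCAL ANESTHETIC INJECTION in your gum, for dental treatment". The answers are yes or no, and neither leads to a skip.
- Item 3 asks: "Compared to INJECTION, how effective do you think was NASAL SPRAY ANESTHETIC in reducing your anxiety and comfort during dental procedure". Its options are "Not Effective Slightly Effective No Difference Very Effective Extremely Effective".
- Item 4 asks how likely the participant is to request the spray "for your future treatment needs (compared to needle anesthetic"), with options "Never No preference Every time".
- No scoring or analysis rule is given for any item.

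In the adult study-visit flow, rescue anesthetic is given at step 10, the MDAS is repeated in all participants at step 12, and the satisfaction questionnaire follows at step 13.

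**The concern.** Acceptability is part of a stated aim, and item 3 is the only printed item in which adults rate the effect they experienced on anxiety and comfort relative to injection. If its answers have no clear meaning, that part of the aim has no usable result.

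Reporting the item descriptively does not solve this. The category counts would be correct counts, but of answers to an ambiguous question. Because scoring is left open, the headline percentage would also depend on a choice made after the data are seen.

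**Working it through.** The plan states no figure for this item, so there is none to reproduce. The check is a reading of the wording, plus simple arithmetic on possible scorings.

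**1. Stem.** 'Reducing' governs both anxiety and comfort. A participant who felt calmer and equally comfortable has no single right answer. Read literally, a high rating is favourable for anxiety and unfavourable for comfort.

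**2. Response labels.** The stem is comparative. Four labels are absolute grades of effectiveness and one ('No Difference') is comparative. It stands third of five, above 'Slightly Effective' and below 'Very Effective'. Labels stating that the spray was worse: 0 of 5. A participant who found it worse than injection can only choose 'Not Effective', the same box as someone who found that it did nothing.

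**3. Effect of the undefined scoring.** Suppose, for illustration only, that all five options are used equally (20% each).

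- Any label containing 'Effective' other than 'Not Effective' counts as favourable: 3/5 = 60%.
- Only options above the printed midpoint count as favourable: 2/5 = 40%.
- Difference from the scoring rule alone: 60% − 40% = 20 percentage points. In general it equals the share choosing 'Slightly Effective'.

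**4. Effect on a mean, if someone codes the item 1 to 5.** Let s be the share choosing 'Slightly Effective' and d the share choosing 'No Difference'. Printed order gives these 2 and 3; with the two swapped they score 3 and 2. The change in the mean is s(3 − 2) + d(2 − 3) = s − d.

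- Assumed s = 0.30, d = 0.10: the mean rises by 0.20.
- Assumed s = 0.10, d = 0.30: the mean falls by 0.20.

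The misplaced label can therefore lower or raise the spray's score.

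**5. Who answers.** Each population is planned with 45 Kovanaze participants and two populations are adult: 2 × 45 = 90. Anyone answering 'No' to item 1 is still asked to compare with injection. The documents do not say how many that would be. Item 1 also cannot isolate earlier experience. Rescue is articaine deposited at the tooth apex (Primary Outcome Measure in Adults) and comes before the questionnaire, so a rescued participant could answer 'Yes' on the strength of that visit alone. Item 2 does not separate these cases, because its most recent category is less than a month ago.

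**The case against.** The strongest reply is that this is one of eight study-specific questions, asked in one arm with no between-arm comparison. The Outcomes section gives the survey's purpose as its effect on patients' confidence in seeking care, which items 7 and 8 address more directly. Anxiety is measured in both arms by the MDAS before and after treatment, and side effects by the 24-hour survey. All of that stands and limits the reach of the point. It does not repair item 3: the five printed MDAS items ask about anxiety in dental situations, and none asks about comfort or about the spray.

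A reader might infer three stronger things that the documents do not support.

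- *That item 3 is the only direct comparison of spray with injection, so dissatisfaction cannot be recorded.* Item 4 is also an explicit comparison, with a neutral option and an option against the spray. It concerns future preference, though, not the effect experienced. Items 6 and 7 also allow unfavourable answers, without naming injection.
- *That the item is biased towards the spray.* The missing 'worse' option points that way. But if 'No Difference' is read as a midpoint, two options fall on the unfavourable side; coding in printed order penalises 'Slightly Effective'; and the literal stem makes a high rating partly unfavourable.
- *That the plan will analyse an invalid 1-to-5 score.* No such score is stated, and category counts need none.

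**Conclusion.** The point holds as a defect of one descriptive item in the adult Kovanaze arm (90 planned). As printed, item 3 does not yield an interpretable comparison of the spray with injection for anxiety or comfort. A tilt towards the spray is possible, but neither its net direction nor its size can be established, because the plan gives no scoring rule and there are no response data. The 20-point swing illustrates the dependence on scoring; it does not estimate bias.

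The conclusion assumes that the form used in clinic prints the stem and options as the protocol does. It also counts only printed items: the MDAS section mentions study-specific questions 6 to 8 on anxiety, but the scale shown ends at question 5. The importance is low, and nothing here touches the primary outcome.

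**What to change.** Before use:

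1. Replace item 3 with two items, one on anxiety and one on comfort. Give each the ordered options 'much worse', 'somewhat worse', 'no difference', 'somewhat better' and 'much better than injection'.
2. Reword item 1 to ask about injections before today's visit, so that a rescue injection at the same visit does not count.
3. Report the two comparisons only in participants who answer 'Yes' to the reworded item 1, and give the number excluded.

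If data are already collected, report the raw count in each of the five categories, with no ordinal score, mean or collapsed 'effective' percentage, and state the limitation.

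The cost is one extra question and a reworded form. The questionnaire is specific to this study, so no validated scale is disturbed. Sample size, visits and procedures do not change.

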Title: Kovanaze Vs. Articaine in Achieving Pulpal Anesthesia of Maxillary Teeth

NCT #: NCT03962634

Document date: 08/28/2019

Document Type: Protocol and Statistical Analysis Plan

Kovanaze vs. Articaine in Achieving Pulpal Anesthesia of Maxillary Teeth: A Randomized, Open-label, Non-Inferiority Trial

Background:

The words a common man would associate with a dentist are 'pain', 'drill' and 'needle'. This association is unfortunate for dentists because a majority of dental procedures require local anesthesia to ensure patient safety and comfort. In clinical dentistry, local anesthetics are directly injected in various sites of the mouth.

Studies have shown that it is the psychological aspect of seeing the needle or expecting a needle to enter the mouth that scares most patients. From a patient's perspective, the needle has been identified as the most fear provoking part of the dentists' armamentarium. The sight of a sharp, metallic needle entering a protected part of the body greatly increases the anxiety and triggers the 'fight or flight' response. The resulting release of adrenaline might be as much as 40 times the normal levels. This adrenaline burst can result in syncopal episodes that accounts for more than half of medical emergencies in dental practice. Heart attacks and strokes can occur in patients suffering from cardiovascular diseases (hypertension, myocardial infarction, angina, arrhythmia). [1] It is recommended that more medically compromised the patient is, more efforts should be made to reduce anxiety. [2]

The aspirating syringe and needle used today was introduced around 150 years ago. [3] It is estimated that up to 40 million Americans avoid visiting the dentist because of fear of pain and anesthetic injections. [4-6] One study found most patients view the injection as the only painful part of the dental procedure. [7]

In June 2016, an intranasal delivery system of local anesthesia called Kovanaze, gained FDA approval. [8] Kovanaze is available as a 0.2 ml metered spray and is intended to achieve pulpal anesthesia of 5 maxillary teeth on either side of the face. Even though success rates between 83 and 90 % have been reported for adults and children >40kg, FDA label (Section 14.2) provides data for children (>10 kg) indicating that the drug is safe for use in children as long as the dose is adjusted to bodyweight of the child. [9]

- One 0.1 mL spray for patients weighing 10 kg to less than 20 kg;

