- b. Mild pain was defined as greater than 0 mm and less than or equal to 54 mm. Mild pain included the descriptors of faint, weak, and mild pain.
- c. Moderate pain was defined as greater than 54 mm and less than 114 mm.
- d. Severe pain was defined as equal to or greater than 114 mm. Severe pain included the descriptors of strong, intense, and maximum possible.

If study participants experience pain/ sensitivity/ discomfort at any time during the procedure (VAS >54), the local anesthesia would be considered a failure and rescue anesthetic (0.7 ml of articaine deposited at the periapex of the tooth of interest) administered to complete the intended procedure.

Secondary Outcome Measures in Adults:

- 1. Onset of meaningful anesthesia:** Patient will be given a stopwatch and will be instructed to press the watch at two different time points:
 - a. Onset of anesthesia (T-1 in min): Press the watch when they first perceive pain relief after the administration of local anesthetic
 - b. Significant pain relief (T-2 in min): Press the watch the second time when the patient report significant pain relief (<54 in VAS scale)

At each time of the stopwatch/ timer, the patient will record their pain in VAS scale. Treatment will proceed as long as the VAS rating is below 54mm. i.e. no to mild pain. If the pain is moderate to high at any point of the procedure (score of 54 or higher), the event would be considered anesthetic failure and a rescue anesthetic administered.

2. Spread of anesthesia:

The teeth and the soft tissues on the side of the mouth ipsilateral to the tooth of interest will be evaluated for spread of anesthesia. The number of teeth that are anesthetized will be counted after cold and electronic pulp tests and recorded (maximum possible score is 5). Similarly, the buccal and lingual gingiva will be tested for anesthesia 1 cm below the gingival margin for each of the 5 teeth ipsilateral to the tooth of interest (maximum score of 5). The hard tissue and soft tissue scores will be compared between two groups.

3. Duration and depth of anesthesia:

In addition to the initial onset, we would gather information about the depth of anesthesia (as tested by EPT and cold tests) at 15 min, 30 min and 1 hour after administration of anesthesia. This would help us identify the duration for which reliable pulpal anesthesia is maintained.

4. Anxiety in Adults:

Modified Dental Anxiety Scale (MDAS):

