5. What is the most important deciding factor for you to choose NASAL SPRAY ANESTHETIC for your dental needs?

Cost Fear and Anxiety

6. How much extra money would you be willing pay for the NASAL SPRAY ANESTHETIC?

\$20 \$50 Up to \$100 It is not worth paying extra

7. Did your experience with the NASAL SPRAY ANESTHETIC change your outlook towards receiving future dental care?

Nothing changed; Still scared of dental visits This appointment was better but am still concerned about my future visits This appointment definitely eased my apprehension of future dental visits

8. If you had known that there was an option of NASAL SPRAY ANESTHETIC, would you have sought dental care early?

Definitely No Maybe Definitely Yes

5. Survey after 24 hours:

A short one question about the side effects of local anesthetic will be asked to the patient in person or over phone at 24 hours.

Did you suffer any of the following side-effects after your dental visit?

- nasal drainage,
- nasal congestion,
- burning,
- pressure,
- sinus congestion,
- pain and soreness at the site of the anesthesia (scored from 1-10)
- Numbing or tingling in throat
- other (Specify)_____

Flow of research study visit in adults (>18 years):

Screening of EHR will be done to identify potential study participants on a routine clinical visit. During the study visit the study related procedures would be preformed in the following order:

1. Go over the study details, answer participant questions and obtain informed consent
2. Administer MDAS anxiety survey
3. Ask patient to rate pain (if present) in the Heft Parker Scale
4. Reveal allocation (Kovanaze or Articaine)
5. Take baseline BP and heart rate
6. Administer local anesthetic
7. Wait for patient to signal achievement of meaningful anesthesia (using stop watch)
8. Map the extent of soft tissue and hard tissue anesthesia in data collection form
9. Proceed with the intended procedure
10. Assign anesthetic **failure** if subject perceives pain after start of procedure. Record the failure in data collection form and proceed with rescue anesthetic to complete the procedure
11. Assign anesthetic **success** if local anesthesia was adequate to complete the intended procedure without need for rescue anesthetic. Record in data collection form
12. Administer MDAS survey for all participants
13. Administer satisfaction questionnaire to subjects in Kovanaze group only
14. Take end of appointment BP and heart rate

Primary Outcome Measure in Children:

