Proportion of study participants in whom intended dental procedure could be successfully completed without the need for rescue anesthetic. We will use a 7 point pictorial emoji scale for children. [6] Each patient will rate his or her initial pain on this pictorial scale and will be asked to place a mark on the scale where it best described their pain level both at the start and any time during the procedure. A cut off point of 4 will be chosen to consider anesthetic failure (anything less than 4 will be interpreted as painful).

Secondary Outcome Measures in Children:

1. Onset of meaningful anesthesia:

Patient will be given a stopwatch and will be instructed to press the watch at two different time points:

- a. Onset of anesthesia (T-1 in min): Press the watch when they first perceive pain relief after the administration of local anesthetic
- b. Significant pain relief (T-2 in min): Press the watch the second time when the patient report significant pain relief (>4 in Emoji scale)

At each time of the stopwatch/ timer, the patient will record their pain in VAS scale. Treatment will proceed as long as the Emoji rating is below 4. i.e. no to mild pain. If the pain is moderate to high at any point of the procedure (score >4), the event would be considered anesthetic failure and a rescue anesthetic administered.

2. Spread of anesthesia:

The teeth and the soft tissues on the side of the mouth ipsilateral to the tooth of interest will be evaluated for spread of anesthesia. The number of teeth that are anesthetized will be counted after cold and electronic pulp tests and recorded (maximum possible score is 5). Similarly, the buccal and lingual gingiva will be tested for anesthesia 1 cm below the gingival margin for each of the 5 teeth ipsilateral to the tooth of interest (maximum score of 5). The hard tissue and soft tissue scores will be compared between two groups.

3. Anxiety and Behavior Score in Children:

Two validated questionnaires will be used in children to assess their anxiety and behavior.

a. STAI-Y6 short form Questionnaire:

Participants will be requested to fill in the short form of the State-Trait Anxiety Inventory questionnaire (STAI: Y6 item) before and after the dental appointment. (Marteau et al.)

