2. Mild, soft verbal protest or (quiet) crying as a signal of discomfort, but does not obstruct progress. Appropriate behavior for procedure, i.e., slight start of injection, "ow" during drilling if hurting, etc.
3. Protest more prominent. Both crying and hand signals. May move head around making it hard to administer treatment. Protest more distracting and troublesome. However, child still complies with request to cooperate.
4. Protest presents real problem to dentist. Complies with demands reluctantly, requiring extra effort by dentist. Body movement.
5. Protest disrupts procedure, requires that all of the dentist's attention be directed toward the child's behavior. Compliance eventually achieved after considerable effort by dentist, but without much actual physical restraint. (May require holding child's hands or the like to start). More prominent body movement.
6. General protest, no compliance or cooperation. Physical restraint is required.

Flow of research related procedures on study visit in children:

Screening of EHR will be done to identify potential study participants on a routine clinical visit. During the study visit the study related procedures would be performed in the following order:

1. Go over the study details, answer participant questions and obtain informed consent
2. Administer STAI-Y6 questionnaire
3. Ask patient to rate pain (if present) in the Emoji Scale
4. Reveal allocation (Kovanaze or Articaine)
5. Take baseline BP and heart rate
6. Administer local anesthetic
7. Wait for patient to signal achievement of meaningful anesthesia (using stop watch)
8. Map the extent of soft tissue and hard tissue anesthesia in data collection form
9. Proceed with the intended procedure
10. Assign anesthetic **failure** if subject perceives pain after start of procedure. Record the failure in data collection form and proceed with rescue anesthetic to complete the procedure
11. Assign anesthetic **success** if local anesthesia was adequate to complete the intended procedure without need for rescue anesthetic. Record in data collection form
12. Record patient anxiety and behavior using Venham scale
13. Take end of appointment BP and heart rate

References:

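### The 24-hour side-effect survey is listed only among the adult outcomes, so as placed the children would have no structured post-visit side-effect data in either arm

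*Combined protocol and SAP*

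**What the plan says.** Specific Aims, item 2, is to "Evaluate patient anxiety, tolerance and acceptability of Kovanaze in patients undergoing dental procedures". It names no age group, and item 1 of the same section includes children from 6 years of age. Population 1 is children aged 6 to 17 years, one of three populations of equal planned size.

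The section "Secondary Outcome Measures in Adults" ends with item 5, a survey after 24 hours. It is a single question: the "side effects of local anesthetic will be asked to the patient in person or over phone at 24 hours". Its checklist covers several nasal and sinus effects, burning, pressure, soreness where the anesthetic was given (scored 1 to 10), throat numbness or tingling, and a free-text entry. The next section is "Flow of research study visit in adults (>18 years)", and the children's outcomes come after that.

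The section "Secondary Outcome Measures in Children" has three items: onset, spread, and anxiety and behavior. For the third, "Two validated questionnaires will be used in children to assess their anxiety and behavior": the STAI-Y6 and the Venham ratings. No item asks about side effects, and no contact after the visit is described. The document has no adverse-event or safety section that applies across populations.

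**The concern.** The checklist shows which local effects the sponsor considered worth asking about for these two anesthetics. Someone running the pediatric part of the study from the children's sections would find no instruction to ask about any of them.

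Two things are at stake. First, the tolerance element of Specific Aim 2 could not be answered for local and delayed effects in children, either for Kovanaze alone or in comparison with articaine. Second, the information is hard to recover: if nobody asks at about 24 hours, later recall or spontaneous complaints are not a systematic substitute. The trial would report on anesthetic success in children with no planned side-effect profile beside it.

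**Working it through.** The plan states no figure on this point, so the main check is to set the adult and children's sections side by side.

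| Item | Adults | Children |
|---|---|---|
| Onset of anesthesia | listed | listed again |
| Spread of anesthesia | listed | listed again |
| Duration and depth | listed | not listed |
| Anxiety | MDAS | STAI-Y6, Venham (also behavior) |
| Satisfaction questionnaire | Kovanaze arm | not listed |
| 24-hour side-effect survey | listed (item 5) | not listed |
| BP and heart rate, start and end of visit | in visit flow | in visit flow |

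1. Onset and spread, which apply to both age groups, are written out twice in nearly the same terms. The survey is written out once, in the adult list. The natural reading is that it belongs to adults.

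2. Nothing else fills the gap. The emoji pain ratings, STAI-Y6, Venham ratings, blood pressure and heart rate are all taken around the appointment. None asks about nasal, throat or injection-site effects, and none can pick up an effect that appears after the child has left. The satisfaction questionnaire has no side-effect item, and the Outcomes section restricts it to adults who receive Kovanaze.

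3. Number affected. The sample-size section gives 45 Kovanaze and 45 articaine participants, 90 together. Its next sentence recruits 100 in each population and 300 overall, so I read the 90 as the size of one population.
   - Children: 45 + 45 = 90.
   - All populations: 3 × 90 = 270, so the share is 90/270 = one third.
   - Kovanaze recipients: 3 × 45 = 135, of whom 45 (one third) are children.

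4. What a survey of 45 Kovanaze children could show, for illustration only. The documents give no side-effect rates, so the true rates below are assumptions, and every child is assumed to answer.
   - If no child reports a given effect, the one-sided 95% upper bound on its rate is 1 − 0.05^(1/45) = 6.4%.
   - The chance of seeing an effect at least once is 1 − (1 − r)^45. For r = 2% it is 60%, for r = 5% it is 90%, and for r = 10% it is 99%.

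   Non-response would widen the bound and lower these chances. The figures show only that a sample of this size is informative about common local effects.

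**The case against.** The strongest reply is that the plan never says the survey is for adults only. Its sentence refers to the patient, with no limit by age or arm. Where the protocol wants a restriction it often labels one: the anxiety item is marked for adults and the satisfaction questionnaire for Kovanaze participants. The numbering in that block is also unreliable, since two items carry the number 4. This stands in part. Adult-only scope is inferred from placement. Even so, the children's list repeats the shared items and omits this one, so the best that can be said for the plan is that its scope in children is unclear, and that also needs correcting.

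The second reply is that children do have tolerability evidence. This also stands in part. Aim 2 does not define tolerance, and pain during the procedure, anxiety, behavior and vital signs all bear on it, in both arms. What is missing is narrower: a structured record of local side effects after the visit. A reader might infer that Population 1 has no tolerability comparison at all. The documents do not support that. Nor does the gap touch the non-inferiority comparison, whose outcome is completion without rescue.

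Two further inferences are tempting and should not be drawn.
- The children's visit flow closes with the step "Take end of appointment BP and heart rate", which might look like proof that nothing later is collected. The adult flow closes with the same step and also omits the survey, and both flows describe only the visit itself. The step proves nothing either way.
- The Background says "success rates between 83 and 90 % have been reported for adults and children >40kg", which might suggest thinner experience in smaller children. That clause concerns efficacy, and the same sentence goes on to cite label data on safety in children above 10 kg with weight-adjusted dosing. The Background does not say that experience is less. Equally, outside safety data do not answer this trial's own tolerance aim or give a comparison with articaine.

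**Conclusion.** The point holds in a limited form. Read as placed, the plan leaves about 90 children, 45 per arm and one third of those planned for analysis, without structured post-visit data on nasal, throat and injection-site effects. Specific Aim 2 covers tolerance in all patients.

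This rests on three readings: that the survey's position in the adult block sets its scope, that the 90 in the sample-size section describes one population, and that no safety collection is described elsewhere in the document. The first is an inference. If the sponsor meant the survey to include children, the defect is one of drafting, and the same edit repairs it. The 6.4% bound depends on zero events and full response; it does not measure damage to any planned analysis. The change is worth making because it is cheap and secures data that the stated aim needs.

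**What to change.** Add the same 24-hour question to the secondary outcomes in children, for both arms of Population 1, answered by the child with a parent. Describe it as a post-visit contact placed after each of the two visit flows, adult and children's, so that staff in all three departments see it. Report the number contacted and the number answering in each arm, so that the denominators are clear.

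The cost is one short call or in-person question per child: about 90 for the children analyzed and up to about 100 for those recruited, using the existing question. The downside is some non-response, and answers given partly by a parent, which should be recorded as such.

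If children were left out on purpose, say so in the plan and limit the side-effect part of the tolerance aim to adults.

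### The only side-effect question asks about the time after the visit and is listed for adults only, so reactions that begin and end in the chair may go unrecorded and tolerability may be overstated

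*Combined protocol and SAP*

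**What the plan says.** Specific Aim 2 is to "Evaluate patient anxiety, tolerance and acceptability of Kovanaze in patients undergoing dental procedures".

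The side-effect instrument is item 5 of the Secondary Outcome Measures in Adults, the survey after 24 hours. The plan introduces it by saying "A short one question about the side effects of local anesthetic will be asked", in person or by phone. The question is "Did you suffer any of the following side-effects after your dental visit". The options are nasal and sinus symptoms, burning, pressure, site pain and soreness scored 1 to 10, "Numbing or tingling in throat", and an open category.

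In both visit flows the anesthetic is given at step 6. In adults, the later steps are the onset signal, step 8 ("Map the extent of soft tissue and hard tissue anesthesia in data collection form"), the procedure, the success or failure assignment, the MDAS, the satisfaction questionnaire (Kovanaze arm only) and step 14 ("Take end of appointment BP and heart rate"). The children's flow matches up to the success or failure assignment, then ends with step 12 ("Record patient anxiety and behavior using Venham scale") and closing blood pressure and heart rate. The Secondary Outcome Measures in Children contain no counterpart to the 24-hour survey.

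**The concern.** Most of the listed symptoms are local reactions to giving the drug, so some could start soon after dosing. The whole dental procedure then takes place before the patient leaves. A question confined to the period after the visit can miss a reaction that starts and ends in the chair, and no other listed step asks about it. A missed reaction lowers the recorded side-effect rate, so the treatment looks better tolerated than it was. This applies to the spray and to the injection. If the share of short-lived reactions differs between arms, the comparison between them is distorted as well. Symptoms not noted at the time cannot be reliably recovered later.

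**Working it through.** The plan gives no figure on this point to reproduce. The check is a reading of the instruments against the timeline, followed by an illustration.

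**1. The interval left out.** Dosing is at step 6, and everything up to step 14 (adults) or step 13 (children) happens at the same visit. Adult secondary outcome 3 tests depth of anesthesia at 15, 30 and 60 minutes after dosing. If those tests are done at the visit, the interval outside the literal wording is about an hour or more.

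**2. What is recorded in that interval.**

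| Measure | Who | Records nasal, throat or site reactions? |
|---|---|---|
| Blood pressure and heart rate, before dosing and at the end | Both arms, both flows | No |
| Pain ratings at the stopwatch presses and during the procedure | Both arms, both flows | No; they serve onset and anesthetic success |
| Venham anxiety and behavior scale | Children, both arms | No; it rates distress and cooperation |
| Satisfaction question 3: "how effective do you think was NASAL SPRAY ANESTHETIC in reducing your anxiety and comfort during dental procedure" | Kovanaze adults only | No; it asks about anxiety and comfort, with no comparison arm |

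The open category in the 24-hour survey sits under the same stem. It widens the type of effect, not the period.

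**3. Who is asked.** Each population has 45 + 45 = 90 participants. Populations 2 and 3 give 2 × 90 = 180 planned adults, 90 per arm, who are asked the question. The 90 planned children of Population 1 have no listed side-effect question. These are counts of people asked or not asked, not of people misclassified.

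**4. Illustration of size (assumed inputs).** Let p be the true share with a reaction, and f the share of those whose reaction resolves before discharge and is not reported. Then

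recorded rate = p × (1 − f).

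| p | f = 10% | f = 25% | f = 50% | f = 75% | f = 90% |
|---|---|---|---|---|---|
| 10% | 9% | 7.5% | 5% | 2.5% | 1% |
| 30% | 27% | 22.5% | 15% | 7.5% | 3% |
| 40% | 36% | 30% | 20% | 10% | 4% |
| 50% | 45% | 37.5% | 25% | 12.5% | 5% |

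For 90 Kovanaze adults and p = 40%, 90 × 0.40 = 36 would react. The expected number recorded is 36 × 0.9 = 32.4, 36 × 0.5 = 18 or 36 × 0.1 = 3.6 for f = 10%, 50% or 90%. If both arms had p = 40% but f were 50% in one and 10% in the other, the survey would show 20% against 36% with no true difference.

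The documents give neither p nor f, so no cell can be called the expected one.

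**The case against.** The best defence is that the wording need not be read strictly. The survey is introduced as being about side effects of the local anesthetic, and it includes throat numbness and an open category. A patient phoned the next day may well mention burning felt in the chair. Effects that last beyond discharge are covered in adults on any reading. Vital signs, pain ratings and the Venham scale also give some in-visit safety and tolerance data. The data collection form named in the flows is not reproduced, and it may hold a side-effect field.

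Much of this stands, and it limits the point. A reader might infer that in-visit reactions are not captured at all, or that the trial will certainly report falsely low rates. The documents support neither: some patients will answer broadly, persisting effects are asked about in adults, and bias is a risk of unknown size rather than a demonstrated result. Nor do they show that the loss would favour the spray over the injection.

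It does not remove the point. If some patients answer for the whole visit and others only for the time afterwards, the reported rate has no defined window, and in an open-label trial the reading could differ by arm. The other in-visit measures do not record nasal or throat symptoms. A possible field on an unseen form is no substitute for a step in the plan.

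**Conclusion.** The point holds as a risk of under-recording. The plan's one side-effect question leaves the period from dosing to discharge either excluded or undefined, neither flow lists a step that fills it, and children have no listed side-effect question at any time. Recorded side-effect rates may be too low and tolerability overstated, in either arm. The size cannot be calculated. In the illustration a 40% true rate is recorded as anything from 36% to 4%, depending wholly on the assumed share of reactions that resolve and go unreported. If few reactions are that brief, or most patients answer broadly, the loss is small.

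This should be corrected because a stated aim depends on it. It does not touch the primary outcome, the sample size or the non-inferiority comparison.

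**What to change.** 1. Reword the 24-hour question to ask about effects *at any time since you were given the dental anesthetic (nasal spray or injection)*.
2. Add one step before discharge to both flows that applies the same short checklist in both arms. At the 24-hour contact, note for each effect whether it began before or after discharge.
3. List the 24-hour question among the children's outcomes too.
4. Report in-visit and post-visit side-effect rates separately, by arm.

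The cost is a wording change and a one-page checklist at a visit already attended, an estimated 1 to 2 minutes per participant, plus a 24-hour contact for the children. Reported side-effect rates will be higher.
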